2.2 Interim Monitoring

Efficacy. The trial is designed specifically to collect three years of data, because of

interest in whether the treatment effect is durable after the first. However, in case of a large effect found after one year, it may be desirable to expand treatment to all communities.

A single interim analysis conducted at alpha of 0.001 will be conducted. Specifically, the interim analysis will be conducted when mortality data are available for the first year (two study periods).

The final analysis would be conducted at alpha 0.049.

Futility. An interim analysis of futility is proposed, to be finalized in consultation with the Data and Safety Monitoring Board. Specifically, we propose to conduct negative binomial regression on village-level mortality counts comparing the treatment and control arms (using a common aggregation parameter) using only data from the first year. This analysis will be conducted using simulation. We suggest consideration of the conditional power to detect a 30% effect. If this drops below 20% at the interim analysis, discontinuation of the trial or other changes to the protocol may be made in consultation with the Data and Safety Monitoring Board.

Interim analysis will be executed by the trial biostatistician at the central site.

3 Sample Size Considerations

We use the following formula (cited from [?]):

$$c = 1 + (z_{\alpha/2} + z_{\beta})^2 \frac{(\lambda_0 + \lambda_1)/y + k^2(\lambda_0^2 + \lambda_1^2)}{(\lambda_0 - \lambda_1)^2}$$

where

c is the number of clusters per arm,

y is the number of person-years per cluster,

λ_0 is the rate in the control group,

λ_1 is the rate in the treatment group,

k is the coefficient of variation in both groups,

α is the alpha level,

β and is the type II error rate.

- The base rate for mortality is assumed to be 0.02 per year in the target age range.
- We assume the same coefficient of variation for village-level mortality as for the Niger site, i.e. 0.34.
- We assume that 16.7% of the population is in the target range of 1–59 months.
- We assume an average community size of 1000 people.
- We assume 10% loss to follow-up per year.
- The effect size is 0.1365.

The number of clusters per arm for Burkina Faso is 170, and the total number of clusters for Burkina Faso is 340.

The sample size is fixed at 341 clusters at the begining of the study.

We estimate that 341 clusters will provide 80% power to detect a 13.65% reduction in mortality in 1-59 month age group.

Power for secondary outcomes

All analyses assume a two-sided alpha of 0.05 and are anticipated to provide a power of at least 80%.

nutritional status The proposed sample size will be sufficient to detect a standardized effect size of 0.108 for weight and height (in the HDSS communities), and of 0.0401 for MUAC (in all communities). We assume an ICC of 0.015.

malaria We assume a placebo parasitemia of 0.2 and an ICC of 0.056. We anticipate at least 80% power to detect a difference of 0.083 between the arms.

antibiotic resistance We assume a placebo drug resistance of 0.05 and an ICC of 0.1. We anticipate at least 80% power to detect a difference of 0.082 between the arms.

4 Randomization

Of the 341 communities available in Nouna district, 48 of these fall within an existing HDSS. We will **stratify** the randomization within this group.

Considering only the 48 HDSS communities, note that an unstratified randomization which allocated each community to **Azithro** with probability 1/2 would yield an approximate 3:2 or worse imbalance (in either direction) with a probability of approximately 8.2%.

The randomization will be conducted using R. The function `sample` with option `replace=FALSE` will be used to conduct the random shuffle. Note that the choice of the random number seed completely determines the randomization. To ensure the integrity of the randomization, we will use the procedure we used for MORDOR/Malawi.

5 Abbreviations

ANCOVA Analysis of covariance

DSMC Data and Safety Monitoring Committee

HAZ height for age Z score

HDSS Health and demographic surveillance system

MUAC Mid upper arm circumference

SAP Statistical Analysis Plan

WAZ weight for age Z score

WHZ weight for height Z score

6 Revision History

5 Oct 2018 Another two pre-specified secondary analyses were added: 1. the number of azithromycin doses received; 2. factorial analysis.

1 Aug 2019 Power calculation and sample size updated.

16 Jan 2020 Changed the title to CHAT.

28 Jan 2020 Took the sensitivity analysis out from Statistical considerations under 2.1.1 Mortality Trial at page 5.

15 June 2022 Changed person time calculation to assign 0 person-time to individuals who are lost to followup or missing during the inter-census interval.

13 Feb 2023 Specified interaction on the additive scale; specified the by-phase subgroup analysis.

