15.6 Statistical Monitoring Guidelines

The SC will propose statistical rules for a futility stopping rule (requested by the sponsor) and an efficacy stopping rule at the first DSMC meeting. A decision will be made whether the efficacy stopping rule is appropriate for the relatively short, 2-year study.

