2.1 Planned Analyses

2.1.1 Mortality Trial

The primary prespecified analysis will use the number of deaths in each community as the outcome variable. For analysis, a death is counted when an individual in the target age range 1–59 months is enumerated as alive on census i ($i = 0, 1, 2, 3$) and is not on census $i + 1$ due to death. Census i takes place at the beginning of the study, and each subsequent census takes place approximately six months later.

Primary Analysis.

The primary analysis will be conducted as **negative binomial regression**. The number of person-years (for persons in the target age range) is derived by summing the person-times for each period. The community-level predictor consists of treatment arm for the community. Specifically, the treatment variable is a community level variable, not an individual level variable. The statistical significance assessed by permutation testing at the level of the randomization unit.

Individuals who are in the target age range at the beginning of any study period, but who are no longer in the target age range by the end, are considered to be fully enrolled and contribute the full amount of person-time for that period.

The analysis will be **two-sided**, with a **type I error rate** (alpha) of 0.05.

Statistical considerations.

- Statistical tests will be conducted with Monte Carlo permutation based on the randomization unit. The number of replications will be 10,000, unless the Monte Carlo confidence interval for the P-value includes 0.05. In this case, 10,000,000 will be used, and this fact reported.
- Tests for interaction by age sub-groups and by phase on the additive scale will be conducted to evaluate for statistically significant subgroup differences.
- Model adequacy will be checked by examination of residuals or other goodness of fit tests as needed. Inadequate model fit will prompt us to report alternative models.
- For negative binomial regression, an aggregation parameter of 30 or greater will cause us to re-fit using Poisson regression.
- Multiple imputation will be used in case of missing baseline covariates (if applicable). Missing outcome variables will be handled by sensitivity analysis and reporting of conditional results.

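### SAP 2.1.1 states alpha 0.05 and keys its Monte Carlo rerun rule to 0.05, while SAP 2.2 sets the final primary test at 0.049; the two sections should be aligned

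*SAP*

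**What the plan says.** SAP 2.1.1, under the primary analysis: "The analysis will be two-sided, with a type I error rate (alpha) of 0.05". It does not call this rate overall, and it does not refer to 2.2. The statistical considerations in the same section set the size of the permutation test: "The number of replications will be 10,000, unless the Monte Carlo confidence interval for the P-value includes 0.05". When the interval does include 0.05, 10,000,000 replications are used.

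SAP 2.2, Efficacy: "A single interim analysis conducted at alpha of 0.001 will be conducted". The look is timed for when first-year mortality data (two of the six-month periods) are available. The section continues: "The final analysis would be conducted at alpha 0.049".

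Protocol 15.6 treats the efficacy rule as still to be settled: "A decision will be made whether the efficacy stopping rule is appropriate for the relatively short, 2-year study". Neither document states the final level if the look is dropped.

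**The concern.** The section that defines the primary test names one level, and the interim section names another for the final analysis. No sentence connects them. Someone working from 2.1.1 alone would compare the final P-value with 0.05 and would not know that 0.001 had already been allotted to the one-year look.

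The Monte Carlo rule raises the same issue in operational form. A rerun rule of this kind exists to make sure simulation noise does not decide the result at the significance boundary. It does that only if it is centred on the boundary actually used. If 0.049 governs, the rule is centred 0.001 too high.

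At stake is the decision rule for the primary mortality endpoint, which should be readable without inference and fixed before anyone sees the P-value.

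**Working it through.** **1. Do the levels fit together?** The interim level is 0.001 and the final level 0.049 (SAP 2.2); the stated rate is 0.05 (SAP 2.1.1). 0.001 + 0.049 = 0.050, an exact match and a standard additive split.

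**2. Overall type I error.** For two correlated standard normal statistics the overall error is 1 − P(|Z1| < c1, |Z2| < c2). Here c1 = 3.291 (0.001), and c2 = 1.969 (0.049) or 1.960 (0.05). The SAP does not give the information at the interim, so the correlation r is an assumption. With one third of the person-time at the interim:
- independent increments: r = √(1/3) = 0.58;
- a community effect that persists over the three years, using the variance terms in step 3: r = √(1.631e-4 / 3.278e-4) = 0.71.

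| Correlation | Final test at 0.049 | Final test at 0.05 |
|---|---|---|
| 0.58 | 0.0495 | 0.0505 |
| 0.71 | 0.0492 | 0.0502 |

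An information fraction as low as 0.2 gives 0.0497 and 0.0507.

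**3. Does the sample size show which level was meant?** SAP section 3 gives control rate 0.02, reduction 13.65% (so λ1 = 0.01727), k = 0.34, community size 1000, 16.7% in the age range and 10% yearly loss. It does not state person-years per cluster. I assume y = 167 × (1 + 0.9 + 0.81) = 452.6.

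- (λ0 + λ1)/y = 0.03727/452.6 = 8.235e-5
- k²(λ0² + λ1²) = 0.1156 × 6.983e-4 = 8.072e-5
- sum 1.631e-4, divided by (λ0 − λ1)² = 7.453e-6, gives 21.88
- at 0.05: c = 1 + (1.960 + 0.842)² × 21.88 = 172.7 per arm
- at 0.049: c = 1 + (1.969 + 0.842)² × 21.88 = 173.8 per arm

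Both are near the SAP's 170, so the sample size does not tell the levels apart. With 341/2 = 170.5 clusters per arm, the noncentrality is √(169.5/21.88) = 2.783. Power is Φ(2.783 − 1.960) = 79.5% at 0.05 and Φ(2.783 − 1.969) = 79.2% at 0.049, a difference of about 0.25 points. With y from 407.3 (heavier loss) to 501 (no loss), the difference stays between 0.2 and 0.3 points.

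**4. The rerun rule.** With 10,000 replications, the table shows the estimated P-values whose interval contains each threshold. The SAP gives neither the confidence level nor the interval type; I assume 95% and show three types.

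| Interval | Contains 0.05 | Contains 0.049 | Contains 0.049 but not 0.05, and lies below it |
|---|---|---|---|
| Wald | 0.0459–0.0544 | 0.0450–0.0534 | 0.0450–0.0458 |
| Wilson | 0.0458–0.0542 | 0.0448–0.0532 | 0.0448–0.0457 |
| Exact | 0.0458–0.0543 | 0.0448–0.0533 | 0.0448–0.0457 |

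Example: an estimate of 0.0455 has standard error √(0.0455 × 0.9545/10,000) = 0.0021 and Wald interval 0.0414 to 0.0496. That interval contains 0.049 but not 0.05, so the result would stand on 10,000 replications although simulation error has not placed it clearly below 0.049. At the upper end the rule only causes some unneeded reruns, which do no harm.

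**The case against.** The strongest reply is that nothing conflicts. The levels add exactly to 0.05, and the sentence in 2.2 is the only one that names a level for the final analysis. Protocol 12.6 refers statistical monitoring to the SAP, and Protocol 15.6 contains no competing alpha. On this view 2.1.1 gives the total, 2.2 divides it, and a cross-reference would be a courtesy. The Monte Carlo rule is a trigger for precision and does not declare significance. It also already sends every estimate between 0.049 and 0.050 to the larger run.

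Most of this stands. A reader might infer that a final P-value such as 0.0495 is both significant and not significant, or that the plan inflates type I error. The documents do not support either. Under the additive split 0.0495 is simply not significant, and the overall error stays below 0.05. Even the mistaken use of 0.05 at the end would give only 0.0502 to 0.0505.

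Two things survive:
- The additive reading does not repair the rerun rule. If 0.049 governs, the rule is centred on the wrong value, and the gap in step 4 exists because of it.
- The deferral to the SAP leaves a contingency open. Protocol 15.6 allows for the efficacy rule not being adopted, and no text says whether the final level would then return to 0.05.

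**Conclusion.** This is a minor but real defect. SAP 2.1.1 carries a threshold that is not the one for the final decision, and its rerun rule is keyed to that threshold. It is a fault of wording and calibration; type I error control is intact.

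The size is 0.001 of alpha, about 0.25 percentage points of power, and a band of estimates about 0.001 wide (roughly 0.0448 to 0.0457) left unresolved against 0.049. The chance that the final P-value falls between 0.049 and 0.050 is 0.1% under no effect and about 0.25% at the design effect.

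The figures rest on these assumptions: about one third of person-time at the interim, 95% Monte Carlo intervals, and about 452.6 person-years per cluster. The conclusion is not sensitive to any of them. The error calculation covers only the single efficacy test in SAP 2.2.

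**What to change.** In SAP 2.1.1, replace the alpha sentence with wording to this effect: *The overall two-sided type I error is 0.05. Because 0.001 is allotted to the one-year efficacy analysis (section 2.2), the final primary test is significant only if the permutation P-value is below 0.049.*

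Change the Monte Carlo trigger from 0.05 to 0.049 for the final primary test, and state the confidence level of the interval.

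If the efficacy look was not carried out, record that before unmasking and use 0.05 in both places. Enter the change in the SAP revision history.

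The cost is a few sentences and, at most, a longer permutation run. Against a reading of 2.1.1 alone, the final threshold is stricter by 0.001, with about 0.25 points less power; against 2.2 as written, nothing changes.

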1.4. Study Site

[figure not shown]
The study will be conducted in the Nouna District in northwestern Burkina Faso. It is situated about 300 kilometres north-west of Ouagadougou, the capital of Burkina Faso.

Nouna Health District is one of the six districts of Boucle du Mouhoun Health Region and covers the geographical area of Kossi Province in the western part of the country. Nouna is the capital of Kossi province. The health district comprises of the town of Nouna with a total population of 29,297 inhabitants and a rural area of about 235,426 inhabitants.

The multicultural society consists of 15 ethnic groups whereof the major ones are the Mossi, Bwaba, Marka, Samo, Gourounsi and Peuhl ethnic groups. The main socioeconomic activity of the population in the district is farming, similar to the rest of the country. The only exceptions are the Peuhl who are semi-nomadic cattle herders and dairy producers.

The health infrastructure consists of one District Hospital in Nouna (Centre Medical avec Antenne chirurgicale, CMA), and over 34 dispensaries (Centre de Santé et de Promotion Sociale, CSPS). The District Hospital in Nouna covers a population of 300,360 inhabitants. The Health Centers each cover a total population between 2,195 and 34,581 inhabitants. Due to deficient road infrastructure only 69.13% of health facilities are accessible for the DHMT all over the year with a mean distance of 8.48 kms (Nouna District action plan 2012). Targeted treatment will also be done in the district of K. Vigué in the Haut Bassins region and in the district of Banfora in the Cascades region..

Province de la Kossi
Carte Administrative et Sanitaire

Scale :

1000000 0 1000000 2000000 Kilometers

Autor : [name], SIG-TD CRSN
Source : NIG-GIS
Date : may, 21th 2018

Legend :	
■	HDSS localities
●	District localities
Roads	
■	National
—	Regional
—	Communal
.....	track
■	HDSS Area
■	District Area
□	Communes boundaries

4 Chapter 2: Context

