nutritional status Weight, height, and MUAC will be analyzed. MUAC will be compared between arms using clustered linear regression (clustered on community). MUAC will be available in all 341 communities; weight and height will only be available in specific prespecified communities which are located in the HDSS.

malaria Malaria parasitemia is assessed using thick smears. The available data will be the fraction of the sampled children who are positive. This is a longitudinally measured fraction, and we propose modeling this using clustered linear regression on square-root transformed data (with clustered logistic regression as a sensitivity analysis). These data are only available in the 48 HDSS communities.

antibiotic resistance Like malaria parasitemia, phenotypic antibiotic resistance is a binary outcome at the individual level, and a fraction at the community level. The same analytic template as for malaria parasitemia will be used.

microbiome Intestinal and nasopharyngeal microbiome will be assessed. We propose to examine L2-norm (Euclidean) distance using PERMANOVA with permutations at the level of the randomization unit. We will also also examine L1 and diversities (L2 and L1, or Simpson's and Shannon's). This outcome, like malaria and antibiotic resistance, is only available in the 48 communities in the HDSS.

cause of death A verbal autopsy questionnaire for children will be used to collect data for verbal autopsies[?]; details are provided in the MOP. Cause of death will be assigned according to an algorithm based on a published verbal autopsy hierarchy. Cause of death will be compared with the use of the chi-square statistic, with clustering taken into account by community-level, using a permutation test to obtain the p-value.

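### The SAP's 80% power rests on 341 clusters averaging 1,000 people, but the protocol's community count and printed populations for Nouna District do not support that pairing, and neither document reconciles them

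*SAP*

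**What the plan says.** SAP section 3 (Sample Size Considerations) gives a formula for clusters per arm in which "y is the number of person-years per cluster". Its inputs are a control rate of 0.02 per year, a coefficient of variation of 0.34, 16.7% of the population aged 1-59 months, 10% loss per year, and "We assume an average community size of 1000 people". It arrives at 170 clusters per arm, fixes the sample at 341, and concludes: "We estimate that 341 clusters will provide 80% power to detect a 13.65% reduction in mortality".

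The SAP uses the same count elsewhere and calls the clusters communities. Section 2.1.1 states "MUAC will be available in all 341 communities" and section 4 states "Of the 341 communities available in Nouna district, 48 of these fall within an existing HDSS". Significance for the primary analysis is "The statistical significance assessed by permutation testing at the level of the randomization unit". Section 2.2 adds: "The final analysis would be conducted at alpha 0.049".

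The protocol differs on the count. Chapter 3 says that every eligible community in Nouna District is randomised and puts the number at 278. Section 4.1 excludes urban areas and divides any community above 2,000 people into two or more randomisation units. Section 1.4 gives 29,297 people in the town, "a rural area of about 235,426 inhabitants", and 300,360 people covered by the district hospital.

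**The concern.** The formula needs person-years per cluster, and inference is at the randomisation unit. The size that matters is therefore the mean population of a randomisation unit. Pairing 341 clusters with 1,000 people each requires 341,000 people in Nouna District. That is more than any population the protocol prints, even before the town is removed as ineligible. The two further districts cannot supply the difference, because protocol sections 1.4, 3.1 and 5.3 bring them in only for the individually randomised targeted treatment.

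If the average size is too high for 341 units, person-years per unit are overstated and so is power. At stake is the trial's stated planned sensitivity, which readers will use to interpret a null or borderline primary result. So is a basic reporting fact: how many units were randomised.

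**Working it through.** **Inputs (SAP section 3 unless noted).** λ0 = 0.02; λ1 = 0.02 × (1 − 0.1365) = 0.01727; k = 0.34; share aged 1-59 months 0.167; c = 341/2 = 170.5 per arm; two-sided alpha 0.05 (section 2.1.1); three years of follow-up (section 2.2). The SAP does not say how the 10% annual loss enters y. I take 3 × 0.9 = 2.7 retained years per child as an assumption. The range is 2.44 (0.9 + 0.81 + 0.729) to 3.0 (no loss). The low end treats children as a closed cohort and deserves little weight, because eligibility is renewed at each census.

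**Formula.** y = mean size × 0.167 × retained years. V = (λ0 + λ1)/y + k²(λ0² + λ1²). Solving the SAP formula for power: Φ(√[(c − 1)(λ0 − λ1)²/V] − 1.96).

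**Reproducing the SAP.** y = 1,000 × 0.167 × 2.7 = 450.9. V = 0.03727/450.9 + 0.1156 × 0.00069825 = 0.00008266 + 0.00008072 = 0.00016337. Clusters per arm = 1 + 7.849 × 0.00016337/0.00000745290 = 173.1, against 170 stated. Power at 170.5 per arm = Φ(2.781 − 1.960) = 79.4%. Exactly 80% corresponds to 2.78 retained years. The stated figure reproduces, so the calculation is sound and the question is the input.

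**The population check.** 341 × 1,000 = 341,000. Against the protocol's figures this is 45% above the rural 235,426, 29% above rural plus town (264,723), 26% above hospital catchment less town (300,360 − 29,297 = 271,063), and 13.5% above the hospital catchment (300,360).

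**Power with 341 units on the populations as printed** (alpha 0.05):

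| Population | Mean per unit | Power at 2.7 years (2.44 to 3.0) | Reduction detectable at 80% power, 2.7 years |
|---|---|---|---|
| 341,000 (SAP) | 1,000 | 79% (77-81%) | 13.75% |
| 235,426 rural | 690 | 71% (68-74%) | 15.2% |
| 264,723 with town | 776 | 74% (71-76%) | 14.7% |
| 271,063 hospital less town | 795 | 74% (72-77%) | 14.6% |
| 300,360 hospital | 881 | 77% (74-79%) | 14.2% |

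Worked for the rural row: y = 690.4 × 0.167 × 2.7 = 311.3, V = 0.00020044, power = Φ(2.510 − 1.960) = 70.9%. The final alpha of 0.049 lowers each power by about 0.3 points.

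**Allowing for growth.** The populations are undated, and protocol section 1.4 cites a 2012 district plan. Assume they date from 2012 and grew 2-3% a year for seven years (factors 1.149 and 1.230). With 341 units and 2.7 years:

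| Population | Projected | Power |
|---|---|---|
| Rural | 270,430-289,544 | 74-76% |
| Hospital less town | 311,366-333,373 | 78-79% |
| Hospital | 345,019-369,405 | 80-81% |

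**The case against.** The strongest reply is that 341 may simply be a later count of the communities themselves. The SAP calls them communities throughout, says the number is fixed, and logs an update of power and sample size on 1 August 2019. The protocol also plans a pre-census before the study. If both 341 and 1,000 came from such an update, the power stands, and the protocol's 278 and its site description are merely out of date. This possibility stands, and the documents do not exclude it.

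Three stronger readings are tempting but not supported.

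- A reader might infer that 1,000 is the mean before large communities are split and 341 the count after. Over 278 communities the printed populations give means of 847 to 1,080, against 690 to 881 over 341, which looks suggestive. But the rural figure over 278 is 15% below 1,000, while the hospital figure over 341 is only 12% below, so the fit does not discriminate. Neither document says that this is what happened.
- A reader might infer that only 278 units were randomised, which would give 67-73% power at 2.7 years. The SAP fixes 341, so this has little support.
- A reader might take 71% as the true power. That is the rural figure with no growth, near the low end of what the documents allow. The printed populations themselves differ by 13.5% (264,723 against 300,360).

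Other planning inputs matter as much. At 881 people per unit, a coefficient of variation of 0.31 in place of 0.34 restores 80.0%. All eligible communities are randomised, so size could not have been tuned, and the futility rule uses a 30% effect, so it does not depend on this figure. The current SAP is dated after the scheduled month-36 visit, and the confidence interval will show the precision achieved. These points limit the consequence. They do not reconcile the two documents.

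**Conclusion.** The inconsistency is real. The cluster count, the average size and the printed populations cannot all describe the same trial area at the same time, and neither document says which is out of date or what 341 counts. The 80% is arithmetically correct on its inputs, but the documents together do not support those inputs. Against the stated 80%, the plan may be optimistic by 0 to about 9 points: nothing if the hospital-catchment figure is used and has grown since 2012, and about 9 points on the rural figure as printed. This assumes 341 units, 2.7 retained years, and the SAP's own rate, coefficient of variation and age share. The true power is not established. The effect is moderate, and it changes no analysis, enrolment target or decision rule.

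**What to change.** - Reconcile 278 with 341 in both documents. State whether 341 counts randomisation units after splitting or a later number of communities, and use the two terms consistently.
- In SAP section 3, replace the 1,000-person assumption with the mean size per randomisation unit from the pre-census, ideally as children aged 1-59 months, which also removes the need for the 16.7% share.
- State how the 10% annual loss enters y.
- Restate the result, for example: with [N] randomisation units of mean size [m] from the pre-census, [r] retained person-years per child and two-sided alpha 0.049, power for a 13.65% reduction is [p]%, and the reduction detectable at 80% power is [d]%. Use pre-census sizes and the planned rate, not observed deaths, so that this remains a planning calculation.

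The cost is one tabulation of a pre-census that the protocol already plans, plus wording in both documents. No extra enrolment is proposed. The downside is a possibly less favourable stated power.
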